6.1.2 DOSING AND ADMINISTRATION

Rules for assigning patients

Within subject rules (subject progressing through tiers for cohort):

1. If a volunteer experiences severe hypoglycemia (blood glucose <45 mg/dL), they will be assigned a dose 100 U less for the next round and for all subsequent rounds.
2. If a volunteer experiences severe hypoglycemia a second time, they will be withdrawn from the study.

Study wide rules (determine which dose tiers are allowable for all future volunteers):

1. All doses from 0 to 1000 U by increments of 100 U will be eligible for testing in the study.
2. If there is greater than 0.9 probability that a dose has a greater than 0.1 toxicity rate, that dose will be removed for all future cohorts (see below).

Allocation Rules

Initial Allocation and Strategy:

Overall, the philosophy of allocation is to assign as many patients as possible to higher doses, while also limiting exposure to toxic doses. The trial will start the first cohort with 200, 400, 600, 800, and 1000 U.

Allocation Adjustment Rules:

After each hypoglycemic event, we will recalculate the toxicity probabilities for that dose to see if a dose removal threshold has been met.

If a dose meets the criteria for removal, that dose and all higher doses will be removed from future participants and cohorts. For the next cohort or patient within a cohort, the highest additional doses available will be used. For example, if 700 U was removed, then 200, 300, 400, 500, 600 U would be the new future allocation.

If a cohort completes with no observed episodes of dose-limiting toxicity (DLT), the smallest (and any smaller) doses will drop, and the highest unused dose will replace it. For example, after zero episodes of DLT in Cohort 1 at any dose, Cohort 2 will use 400, 600, 800, 900, and 1000 U. Doses 100 and 200 U will be dropped.

If a cohort has any DLT, but no dose is dropped (only 1 DLT in two different doses for example), the initial allocation rules will be used for the next cohort (200, 400, 600, 800, 1000 U).

4 Cohort Example - No DLT (Demonstrated by Schema Figure 1.2.2)

Cohort 1: Participants #1 to 6

The doses will be 0, 200, 400, 600, 800, and 1000 U.

Cohort 2: Participants #7 to 12

If there were 0 events in Cohort 1, then the doses for Cohort 2 will be 0, 400, 600, 800, 900, and 1000 U. 200 U will be dropped and 900 U will be entered.

Cohort 3: Participants #13 to 18

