7 STUDY INTERVENTION DISCONTINUATION AND PARTICIPANT DISCONTINUATION/WITHDRAWAL

7.1 DISCONTINUATION OF STUDY INTERVENTION

The rules for stopping or changing an individual dosing regimen are given above in the Dosing and Administration section.

Rules for discontinuing a dose

We are interested in proceeding with a dose if we remain confident that the Dose Limiting Toxicity (blood glucose < 45 mg/dL) is < 0.1 (1 in 10).

Using the Bayesian Toxicity Monitoring software from MD Anderson (<https://ibl.mdanderson.org/BTM/>)

We define Toxicity parameters as:

Probability of DLT is represented by θ

Maximum probability of DLT allowed (θ_{\max}): 0.1

When calculating the probability of DLT at a dose, we will use a Beta(0.2,0.8) prior. This is a vague prior with a median of 0.2 and a 95% credible interval from 0 to 0.94. There is greater density over probabilities of DLT near zero in this non-symmetric distribution. Each DLT is added to the A parameter of the beta distribution, and each patient who is DLT free is added to the B parameter of the B distribution. Therefore, with the prior included, if 24 participants have DLT on a dose, the probability of DLT can be described with a Beta(0.2,24.8) distribution. In this setting, the posterior estimate for DLT probability is 0.008 (or 0.8%). In addition, the probability that that dose has a DLT proportion over 0.1 is only 0.006 (or 0.6%).

$\text{Prob}(\theta > \theta_{\max}) \geq 0.9$ (Or that there is 90% or greater probability that the DLT is greater than 0.1)

We define the probability that $\text{Prob}(\theta > \theta_{\max})$ as the final output of the trial for each dose. For each dose, we will also calculate the probability that toxicity is greater than 0.1 at that dose.

The below table (SB1A) illustrates the probability that DLT is greater than 0.1 based on the number of observed events.

Table SB1A: Probability of Early Stopping
Number of Toxicities
(Highlighted = Prob(e > 0.1) >= 0.9)

	0	1	2	3	4	5	6	7	8	9	10	11	12	13	14	15	16	17	18	19	20	21	22	23	24
Number of Patients																									
6	.0884	.6292	.9196	.9990	.9993	1.0000	1.0000	NA	NA	NA	NA	NA	NA	NA	NA	NA	NA	NA	NA	NA	NA	NA	NA	NA	NA
12	.0333	.3613	.7196	.9151	.9816	.9971	.9997	1.0000	1.0000	1.0000	1.0000	1.0000	1.0000	NA	NA	NA	NA	NA	NA	NA	NA	NA	NA	NA	NA
18	.0141	.2027	.5135	.7773	.9220	.9786	.9954	.9992	.9999	1.0000	1.0000	1.0000	1.0000	1.0000	1.0000	1.0000	1.0000	1.0000	1.0000	1.0000	NA	NA	NA	NA	NA

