24	.0063	.1123	.3460	.6152	.8189	.9310	.9784	.9944	.9988	.9998	1.0000	1.0000	1.0000	1.0000	1.0000	1.0000	1.0000	1.0000	1.0000	1.0000	1.0000	1.0000	1.0000	1.0000	1.0000

In practice, this means if 2 DLTs are observed for a dose in the first cohort, the dose is dropped. To drop a dose in subsequent cohorts, see the shaded area of the above table. To delete a dose, one must have 3 total observed DLTs in Cohorts 1 and 2, or 4 total DLTs in Cohorts 1-3, or 5 total DLTs in Cohorts 1-4.

Rules for discontinuing or modifying the overall study

There are no binding rules to discontinue the overall study. However, if the 500 U dose tier was dropped, there would only be 100, 200, 300, and 400 U available. In this case, the PI will consult with the other investigators to present an amended plan for future study conduct or overall discontinuation.

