9.2 SAMPLE SIZE DETERMINATION

Overall, for any dose we estimated whether the study would end, with different assumptions of the probability of toxicity for a given dose. These ranged from 0.01 to 0.25. It is possible, however, that a dose tier may not be desirable despite having not been dropped. For example, there will be about an 82% probability that the toxicity rate is > 0.1 if 4 out of 24 participants experience a DLT, then the point estimate using the Bayesian model will be that arm has a 0.17 probability of DLT (slightly above the raw observed rate of 0.125 due to the Bayesian prior).

The design has approximately 80% “power” at the margin (scenario 5). That is, if the true rate of DLT is 0.1 at a dose, the DLT will NOT be declared toxic using the pre-specified definition ($\text{Prob}(\theta > 0.1) \geq 0.9$) just under 80% of the time.

It is important to note that the table below is for a single dose with 24 observations. As the trial progresses, we will generate independent estimates of the probabilities for each dose. The average number of patients indicates that the dose will stop early some proportion of the time. The average number of toxicities provides the average number of DLTs observed within a simulated trial when the true probability of toxicity is given (for example 0.1 in scenario 5).

Table: Operating Characteristics for a Dose Assuming N of 24

Scenario	Prob.Of.Tox	Prob Early.Stop	ProbDeclare.Tox	Avg.N.Patients	Avg.N.Tox	Obs.Tox.Rate
1	0.01	0.0016	0.0016	23.9724	0.2397	0.0104
2	0.025	0.0105	0.0105	23.8235	0.5956	0.0272
3	0.05	0.0453	0.0467	23.2792	1.164	0.0583
4	0.075	0.1062	0.1125	22.3836	1.6788	0.0921
5	0.1	0.1898	0.2062	21.1965	2.1196	0.127
6	0.125	0.2892	0.3196	19.8036	2.4754	0.1617
7	0.15	0.3962	0.4415	18.2978	2.7447	0.1952
8	0.2	0.6031	0.669	15.277	3.0554	0.2563
9	0.25	0.7684	0.8336	12.6203	3.1551	0.3089

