9.4.6 PLANNED INTERIM ANALYSES

The dosing plan for the next cohort will be determined after each cohort completes. Participants within any cohort will have their dosing plan adjusted in the event one of the planned doses for that cohort is dropped due to excess DLTs in the other participants within that cohort.

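### The removal formula applied after each event and the 2/3/4/5-DLT count rule can give opposite decisions, and the Section 9.2 retention figure of about 80% belongs to only one of them

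*Combined protocol and SAP*

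**What the plan says.** **Formula.** Section 6.1.2, study-wide rules: "If there is greater than 0.9 probability that a dose has a greater than 0.1 toxicity rate, that dose will be removed". Section 7.1 gives the calculation: "we will use a Beta(0.2,0.8) prior", with each DLT added to the first parameter and each DLT-free patient to the second.

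**Timing.** Section 6.1.2, where it explains how allocation is adjusted, has: "After each hypoglycemic event, we will recalculate the toxicity probabilities for that dose to see if a dose removal threshold has been met". Section 9.4.6 confirms that removal can act within a cohort: "Participants within any cohort will have their dosing plan adjusted in the event one of the planned doses for that cohort is dropped".

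**Consequence.** Section 6.1.2: "If a dose meets the criteria for removal, that dose and all higher doses will be removed from future participants and cohorts". The same section adds that higher doses, once dropped, cannot come back.

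**Count rule.** Section 7.1, below Table SB1A: "In practice, this means if 2 DLTs are observed for a dose in the first cohort, the dose is dropped". It then asks for 3 DLTs in total over Cohorts 1-2, 4 over Cohorts 1-3 and 5 over Cohorts 1-4. Table SB1A has rows only for 6, 12, 18 and 24 patients.

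**Step-down rule.** Under Section 6.1.2, a participant with severe hypoglycemia receives 100 U less in the next and all later rounds, and is withdrawn after a second event.

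**MTD.** Sections 9.1 and 9.4.1 define it by the formula, as the highest dose below the 0.9 threshold, not by the counts.

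**Operating characteristics.** Section 9.2 reports that a dose with a true DLT rate of 0.10 escapes being declared toxic slightly less than 80% of the time, and states the basis: "It is important to note that the table below is for a single dose with 24 observations".

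**The concern.** Section 7.1 presents the counts as the practical meaning of the formula. That holds when exactly 6, 12, 18 or 24 people have been exposed to the dose. Section 6.1.2 also applies the formula between those points, and the step-down rule creates doses that only one person may receive. At those sample sizes the formula and the counts are different rules.

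Removal is the trial's central decision. It takes out every higher dose, it cannot be undone upward, and it bears directly on the MTD. Staff who see a DLT in the first person given a dose would find one instruction in Section 6.1.2 and the opposite one in Section 7.1. The stated operating characteristics would describe only one of the two resulting trials.

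**Working it through.** **Inputs.** Prior Beta(0.2, 0.8), DLT limit 0.1 and threshold 0.9 (Section 7.1); recalculation after each event (Section 6.1.2); maximum of 24 per dose (Section 9.2). Section 6.1.2 uses a strict inequality and Section 7.1 a non-strict one; no result below depends on this.

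**Formula.** With k DLTs in n people exposed, P(k/n) = Pr(θ > 0.1) under Beta(0.2 + k, 0.8 + n − k), each person counted once per dose.

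**Step 1: the plan's own boundaries.** 2/6 = 0.9196, 3/12 = 0.9151, 4/18 = 0.9220, 5/24 = 0.9310. All match Table SB1A, and they are the source of the counts 2, 3, 4 and 5.

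**Step 2: the formula between those points.**

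| DLTs/exposed | P(θ > 0.1) | Formula | Count rule |
|---|---|---|---|
| 1/1 | 0.9503 | remove | keep |
| 1/2 | 0.8824 | keep | keep |
| 1/3 | 0.8146 | keep | keep |
| 1/6 | 0.6292 | keep | keep |
| 4/19 | 0.9075 | remove | keep (fourth cohort, 5 needed) |

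The 1/1 row is Beta(1.2, 0.8). It applies only when the first person exposed has the DLT.

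**Step 3: a dose given to one person.** Cohort 1 is assigned 200, 400, 600, 800 and 1000 U. Suppose one participant has a DLT at 400 U and the other five do not: 1/6 = 0.629, so 400 U stays under both rules. That participant moves to 300 U, which is not in the cohort's allocation. If nobody else steps down to it, n = 1 at 300 U even when the cohort is complete. A second DLT there is 1/1 = 0.950. The formula removes 300 U and everything above it; the count rule removes nothing. Table SB1A has no row for n = 1.

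**Step 4: the Section 9.2 table.** Exact binomial recursion over n = 1 to 24, with looks only at 6, 12, 18 and 24, reproduces all nine scenarios. For scenario 5 (true rate 0.10) it gives early stop 0.1898, declared toxic 0.2062 and average N 21.1965. Retention is 1 − 0.2062 = 0.7938.

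**Step 5: the same recursion with the formula after each event.** Checking after every participant gives the same decisions, because a DLT-free result only lowers P.

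| True DLT rate | Declared toxic, looks at 6/12/18/24 | Declared toxic, formula after each event |
|---|---|---|
| 0.01 | 0.0016 | 0.0111 |
| 0.05 | 0.0467 | 0.0846 |
| 0.10 | 0.2062 | 0.2595 |

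At 0.10, retention is 1 − 0.2595 = 0.7405, and average N falls from 21.2 to 19.5.

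**Step 6: the source of the shift.** If event-by-event checks could remove a dose only with at least 2 DLTs, the declared-toxic probability at 0.10 would be 0.2123. Of the total increase, 0.2595 − 0.2062 = 0.0533, the 1/1 case therefore contributes 0.2595 − 0.2123 = 0.0472, or 89%. If the Table SB1A denominators are used at each event, the figure stays at 0.2062.

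**The case against.** The strongest reply is that the counts were always meant to govern. Section 6.1.2 points forward to the discontinuation rules in Section 7.1. One of its allocation rules treats single DLTs at two different doses as dropping nothing, and another example keeps the initial allocation when each of the four cohorts has one DLT at a different dose. Recalculating after an event could then mean reading Table SB1A with the full-cohort denominator. On that reading the conflict disappears for planned doses and 0.2062 is unaffected.

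Much of this stands: these passages do suggest that one DLT was not meant to drop a dose. But no section states that denominator. It cannot cover a reduced dose given to one person, where no full cohort exists. And Sections 9.1 and 9.4.1 define the MTD by the formula, so the question returns at the final analysis.

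Three stronger readings are tempting, and the documents do not support them:

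- That any single DLT removes a dose. It does so only in the first person exposed.
- That the 80% figure is wrong or its basis hidden. It is correct for looks at 6, 12, 18 and 24, and Section 9.2 openly describes a single dose with 24 observations.
- That one susceptible participant can shut the trial. Section 7.1 has no binding rule for stopping the study; loss of the 500 U tier leads to consultation and an amended plan.

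**Conclusion.** The conflict is real but narrow. It occurs when the first person exposed to a dose has a DLT, when a reduced dose is given to one person, and at isolated later points such as 4/19. In each case the formula on the number exposed so far removes the dose and all higher doses, while the count rule keeps them.

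For one dose with up to 24 exposures, the reading moves retention at a true rate of 0.10 from 79.4% to about 74%, a difference of 5.3 points. At a true rate of 0.01 it moves the probability of being declared toxic from 0.0016 to 0.0111, about sevenfold but under one percentage point. These figures assume independent DLTs, each person counted once per dose, and no removal caused by a lower dose, which the plan's own table also leaves out.

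A reader might infer a much larger loss across the whole trial. Simulations can show one, but only with dose-specific DLT rates that the documents do not give, and the result under the count rule itself varies with how the counts are applied. No whole-trial figure is therefore part of this conclusion. Nor does it say which removal rule is right.

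**What to change.** Reconcile Sections 6.1.2, 7.1, 9.1, 9.4.1 and 9.4.6 into one binding criterion. It should state which rule governs when formula and counts disagree, which denominator applies at a mid-cohort recalculation, and which applies to a reduced dose given to one person. The choice belongs to the sponsor-investigator.

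Then match Section 9.2 to that choice:

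- If cohort-end looks or the Table SB1A denominators govern, keep the declared-toxic probability of 0.2062 (about 79% retained). Average N and early-stop figures should follow the timing chosen.
- If the formula after each event governs, restate scenario 5 as 0.2595 (about 74% retained), rerun the other scenarios, and revise the Section 7.1 sentences that give the counts.

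A whole-trial simulation that includes removal of all higher doses would be a useful supplement, with its assumed DLT rates stated. It is not needed to resolve the conflict.

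The cost is a protocol clarification and a short recalculation, and possibly a slightly less favourable stated figure. It should be settled before dosing, because a removed higher dose cannot return.

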6.2 PREPARATION/HANDLING/STORAGE/ACCOUNTABILITY

6.2.1 ACQUISITION AND ACCOUNTABILITY

HUMULIN R U-500 (insulin human injection, NDC 0002-8501-01) will be purchased as commercial supply through Eli Lilly and Company. Storage and accountability will be maintained by Research Pharmacy, Michigan Medicine. Diluent to prepare the 0 U/mL dose and lower concentrations of intranasal insulin will be acquired through Eli Lilly and Company (Sterile Diluent, NDC 0002-0800) or similar manufacturer ([contact]).

6.2.2 FORMULATION, APPEARANCE, PACKAGING, AND LABELING

HUMULIN R U-500 is available as single 20 mL multi-use vials. The concentration is 500units/mL

6.2.3 PRODUCT STORAGE AND STABILITY

Unopened vials of HUMULIN R U-500 will be stored in a refrigerator (36° to 46°F [2° to 8°C]) protected from freezing and light, with a do not shake notice. Opened vials of HUMULIN R U-500 will also be stored in a refrigerator (36° to 46°F [2° to 8°C]) protected from freezing and light and used within 40 days then subsequently discarded. Syringes containing ≤1 mL volume at doses of 0 (diluent), 50, 100, 150, 200, 250, 300, 350, 400, 450, and 500 U (undiluted) will be prepared and stored in a refrigerator for no more than four hours total at (36° to 46°F [2° to 8°C]) and/or room temperature, protected from freezing and light. A prior stability study demonstrated at least 28-day stability at this temperature. (18)

6.2.4 Preparation

No special preparation is necessary for HUMULIN R U-500 and sterile diluent measured to the aforementioned doses under a laminar flow hood by Research Pharmacy.

6.3 MEASURES TO MINIMIZE BIAS: RANDOMIZATION AND BLINDING

No randomization or masking procedures will be used in this study.

6.4 STUDY INTERVENTION COMPLIANCE

The study related activities, including drug administration and observation, will be performed with support from the Michigan Clinical Research Unit with an extensive track record of data integrity and compliance with regulatory procedures. Given that participants will be seen weekly, study compliance

will be reviewed at each visit. A record of any study queries, discrepancies, or deviations from the protocol will be maintained and provided to the study site and PI to resolve and document as a part of the study record. There are no subject diaries or study related activities that occur outside of subject visits.

6.5 CONCOMITANT THERAPY

6.5.1 RESCUE MEDICINE

If a subject's blood glucose level falls <45 mg/dL, he/she will be treated with 50 ml of intravenous D50W and provided food. He/she will be monitored until achieving two consecutive measurements of blood glucose > 70mg/dL, measured at 30 minutes apart. If blood glucose falls to ≤70 mg/dL but not <45 mg/dL, the blood glucose will be monitored every 30 minutes until it returns to >70 mg/dL.

7 STUDY INTERVENTION DISCONTINUATION AND PARTICIPANT DISCONTINUATION/WITHDRAWAL

7.1 DISCONTINUATION OF STUDY INTERVENTION

The rules for stopping or changing an individual dosing regimen are given above in the Dosing and Administration section.

Rules for discontinuing a dose

We are interested in proceeding with a dose if we remain confident that the Dose Limiting Toxicity (blood glucose < 45 mg/dL) is < 0.1 (1 in 10).

Using the Bayesian Toxicity Monitoring software from MD Anderson (<https://ibl.mdanderson.org/BTM/>)

We define Toxicity parameters as:

Probability of DLT is represented by θ

Maximum probability of DLT allowed (θ_{\max}): 0.1

When calculating the probability of DLT at a dose, we will use a Beta(0.2,0.8) prior. This is a vague prior with a median of 0.2 and a 95% credible interval from 0 to 0.94. There is greater density over probabilities of DLT near zero in this non-symmetric distribution. Each DLT is added to the A parameter of the beta distribution, and each patient who is DLT free is added to the B parameter of the B distribution. Therefore, with the prior included, if 24 participants have DLT on a dose, the probability of DLT can be described with a Beta(0.2,24.8) distribution. In this setting, the posterior estimate for DLT probability is 0.008 (or 0.8%). In addition, the probability that that dose has a DLT proportion over 0.1 is only 0.006 (or 0.6%).

$\text{Prob}(\theta > \theta_{\max}) \geq 0.9$ (Or that there is 90% or greater probability that the DLT is greater than 0.1)

We define the probability that $\text{Prob}(\theta > \theta_{\max})$ as the final output of the trial for each dose. For each dose, we will also calculate the probability that toxicity is greater than 0.1 at that dose.

The below table (SB1A) illustrates the probability that DLT is greater than 0.1 based on the number of observed events.

Table SB1A: Probability of Early Stopping
Number of Toxicities
(Highlighted = Prob(e > 0.1) >= 0.9)

	0	1	2	3	4	5	6	7	8	9	10	11	12	13	14	15	16	17	18	19	20	21	22	23	24
Number of Patients																									
6	.0884	.6292	.9196	.9990	.9993	1.0000	1.0000	NA	NA	NA	NA	NA	NA	NA	NA	NA	NA	NA	NA	NA	NA	NA	NA	NA	NA
12	.0333	.3613	.7196	.9151	.9816	.9971	.9997	1.0000	1.0000	1.0000	1.0000	1.0000	1.0000	NA	NA	NA	NA	NA	NA	NA	NA	NA	NA	NA	NA
18	.0141	.2027	.5135	.7773	.9220	.9786	.9954	.9992	.9999	1.0000	1.0000	1.0000	1.0000	1.0000	1.0000	1.0000	1.0000	1.0000	1.0000	1.0000	NA	NA	NA	NA	NA
24	.0063	.1123	.3460	.6152	.8189	.9310	.9784	.9944	.9988	.9998	1.0000	1.0000	1.0000	1.0000	1.0000	1.0000	1.0000	1.0000	1.0000	1.0000	1.0000	1.0000	1.0000	1.0000	1.0000

In practice, this means if 2 DLTs are observed for a dose in the first cohort, the dose is dropped. To drop a dose in subsequent cohorts, see the shaded area of the above table. To delete a dose, one must have 3 total observed DLTs in Cohorts 1 and 2, or 4 total DLTs in Cohorts 1-3, or 5 total DLTs in Cohorts 1-4.

Rules for discontinuing or modifying the overall study

There are no binding rules to discontinue the overall study. However, if the 500 U dose tier was dropped, there would only be 100, 200, 300, and 400 U available. In this case, the PI will consult with the other investigators to present an amended plan for future study conduct or overall discontinuation.

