If there were 0 events in Cohorts 1 and 2, then the doses for Cohort 3 will be 0, 600, 700, 800, 900, and 1000 U. 400 U will be dropped and 700 U will be entered.

Cohort 4: Participants #19 to 24

Same as Cohort 3.

Other situations (more than one DLT)

Please also refer below to rules for discontinuing a dose.

If a dose (or doses) is dropped during or after a cohort, the highest available unused doses will be used for the next patients within that cohort and the next cohort. For example, if 1000 U is dropped, the future doses will be 200, 400, 600, 800 and 900 U. Or, if 800 U and all higher doses are dropped, then 200, 400, 500, 600, and 700 U will be the next set.

As one example, if there is 1 DLT in a different dose in each of the 4 cohorts, the trial will simply allocate using the initial rules for all cohorts, with the exception of the within subject adjustment rule noted above.

For example, if there are no DLTs in Cohort 1, then Cohort 2 will use 400, 600, 800, 900, and 1000 U. If Cohort 2 also has no DLTs, then 300 and 400 U will drop and Cohort 3 will use 600, 700, 800, 900, and

1000 U. Even if there are no DLTs in Cohort 3 given that allocation, we will continue that allocation as it utilizes the 5 highest available doses.

If higher doses are dropped, they cannot be reconsidered in the study.

If lower doses are dropped, they can re-enter the study. This would occur if higher doses needed to be dropped by having DLTs over the threshold. The lower doses may need to re-enter in order for each subject to have 5 potential doses.

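### The DLT counts by cohort in Section 7.1 match the 0.9 removal rule only for doses given to about all six participants in every cohort; for later entrants they ask for one to three DLTs too many

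*Combined protocol and SAP*

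**What the plan says.** Section 6.1.2 sets the rule: "If there is greater than 0.9 probability that a dose has a greater than 0.1 toxicity rate, that dose will be removed". Removal holds in every later cohort, and all higher doses go with it. It also sets the timing: "After each hypoglycemic event, we will recalculate the toxicity probabilities for that dose". Section 7.1 gives the calculation, a Beta(0.2, 0.8) prior updated with that dose's own data: "Each DLT is added to the A parameter of the beta distribution, and each patient who is DLT free is added to the B parameter". Section 9.2 confirms that each dose is estimated independently. Table SB1A is indexed by number of patients, with rows at 6, 12, 18 and 24.

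Below the table, Section 7.1 puts the rule into practical terms. Two DLTs in the first cohort drop a dose. For later cohorts it says "To drop a dose in subsequent cohorts, see the shaded area of the above table". The next sentence reads "To delete a dose, one must have 3 total observed DLTs in Cohorts 1 and 2, or 4 total DLTs in Cohorts 1-3", and continues with 5 in Cohorts 1-4.

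Not every dose is in use from Cohort 1. In the no-DLT example of Section 6.1.2, at Cohort 2 "200 U will be dropped and 900 U will be entered", and at Cohort 3 "400 U will be dropped and 700 U will be entered". If 1000 U is removed, 900 U comes in. If 800 U and above are removed, 500 and 700 U come in.

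**The concern.** The posterior depends on how many participants have received the dose, whereas the counts depend on which trial cohort is running. The two agree only if cohort number times six equals the number treated at that dose. For a dose brought in later, the counts ask for more DLTs than the posterior rule does, so two adjacent sentences give opposite instructions on the same data.

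At stake is whether a dose that has met the removal rule stays open to further healthy volunteers, together with every higher dose. Section 7.1 has no binding rule to stop the whole study, so dose removal is the main study-wide safeguard.

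**Working it through.** **Inputs.** From Section 7.1: prior Beta(0.2, 0.8), DLT limit 0.1, cutoff 0.9. From Section 6.1.2: cohorts of six and the entry of doses. The true DLT rates p below are assumptions, shown as a range.

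**Formula.** With x DLTs among n participants treated at the dose, P = Prob(θ > 0.1), where θ follows Beta(0.2 + x, 0.8 + n − x).

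**The plan's figures reproduce.** 2/6 gives 0.9196, 3/12 gives 0.9151, 4/18 gives 0.9220 and 5/24 gives 0.9310, as printed. The counts 2, 3, 4 and 5 are therefore correct at n = 6, 12, 18 and 24. (The cell for 3/6 is printed .9990 and computes to 0.9900; the boundary is unaffected.)

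**Smallest count with P ≥ 0.9, by n.** 2 for n = 2-6 (2/7 gives 0.8906); 3 for n = 7-12 (3/13 gives 0.8955); 4 for n = 13-19 (4/19 gives 0.9075, 4/20 gives 0.8919); 5 for n = 20-24. At n = 1, one DLT gives 0.9503.

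**Sentence against rule, six treated per cohort from entry:**

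| First cohort of use | End of cohort | n at dose | Rule | Sentence | Excess |
|---|---|---|---|---|---|
| 2 | 2 / 3 / 4 | 6 / 12 / 18 | 2 / 3 / 4 | 3 / 4 / 5 | 1 |
| 3 | 3 / 4 | 6 / 12 | 2 / 3 | 4 / 5 | 2 |
| 4 | 4 | 6 | 2 | 5 | 3 |

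So 3/6 for a Cohort 3 entrant (P = 0.9900) and 4/6 for a Cohort 4 entrant (P = 0.9993) would both be kept under the sentence. First entry in Cohort 4 is reachable: DLTs that remove nothing in Cohorts 1 and 2 keep the initial set through Cohort 3, and a DLT-free Cohort 3 then brings in 900 U.

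**Size if staff follow the sentence, entry at the start of Cohort 2.** Exact binomial recursion, six treated per cohort, gives removal by the end of Cohort 4:

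- p = 20%: 0.6031 (rule) against 0.3326 (sentence)
- p = 25%: 0.7684 against 0.5283

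The rule figures equal the early-stop probabilities in Section 9.2, scenarios 8 and 9. Checking after every event instead of at cohort end leaves them unchanged; at 20% the expected number dosed is then 11.9 against 15.6.

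**Size when 900 U replaces 1000 U removed in Cohort 1.** Assumptions: 1000 U is given one participant at a time; its second DLT removes it at participant j = 2 to 6; 900 U goes to the remaining 6 − j and then to six per cohort; checks follow each event; both doses share p; 1/1 does not remove a dose.

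| p | Rule | Sentence | Chance 1000 U is removed in Cohort 1 | Weighted gap |
|---|---|---|---|---|
| 15% | 0.4144 | 0.2247 | 0.2235 | 0.042 |
| 20% | 0.6278 | 0.4297 | 0.3446 | 0.068 |
| 25% | 0.7928 | 0.6343 | 0.4661 | 0.074 |
| 30% | 0.8987 | 0.7959 | 0.5798 | 0.060 |

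At 20% the gap is 0.3446 × (0.6278 − 0.4297) = 0.068. Expected participants given 900 U are 12.55 against 15.64, so the weighted excess is 0.3446 × 3.09 ≈ 1.1.

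**The case against.** The strongest reply is that the plan already gives the right rule several times: the probability criterion and the recalculation after each event in Section 6.1.2, the prior and update in Section 7.1, and the definition of the maximum tolerated dose from the posterior in Sections 9.1 and 9.4.1. The counts follow a pointer to the table and can be read as its rows put into words. Staff who recalculate after each event would have the correct answer in hand. This stands, and it makes every figure above conditional. It does not remove the conflict: the sentence is worded as a requirement, and its cohort numbers are those that Section 6.1.2 assigns to participants 1-6 through 19-24, not a dose's own first, second and third cohorts.

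The sizes also have limits.

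- On the no-DLT path, if 900 U then has DLTs in Cohort 2 and is not dropped, the next cohort returns to the initial set, which has no 900 U. Harm there runs through 1000 U staying open. The 60% against 33% comparison applies where the dose keeps being given.
- In the replacement case, 900 U enters during Cohort 1 in about 76% of the removal paths at p = 20% (1 − 0.238). The mismatch is the same, but this is not entry at the start of a cohort.
- A participant stepped down after a DLT at 800 U does not reach 900 U, so six per cohort is an upper limit.

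A reader might infer that 700 U, entering in Cohort 3, would be wrongly kept a third of the time at a 20% rate, since 2 or 3 DLTs in 6 has probability 0.3446 − 0.0170 = 0.3276. That ignores how the trial gets there. Entry by the no-DLT path needs no DLTs in 12 + 18 = 30 earlier administrations at 800-1000 U. If those doses are at least as toxic as 700 U, the chance is at most 0.8^30 = 0.12% with independent administrations, or 0.8^12 = 6.9% if each participant's outcomes are fully correlated. The joint chance is then at most about 0.04% to 2.3%.

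**Conclusion.** The sentence is wrong as written for any dose not given to about all six participants in every cohort from Cohort 1. The excess of one, two or three DLTs is exact for full cohorts of six. The consequence depends on staff following the sentence over the table or the recalculated posterior. If they did, the loss for a dose entering at the start of Cohort 2 and kept in use is about 27 percentage points of removal probability at a 20% DLT rate and 24 at 25%. For 900 U replacing 1000 U, the gap weighted by the chance of that path is about 4 to 7 points for rates of 15% to 30%, with about one extra participant dosed at 20%.

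A reader might infer that the removal rule or Table SB1A is faulty, or that unsafe doses will in fact stay open. The documents do not support either: the rule, the event-driven recalculation and the table's removal boundaries are correct. The within-subject step-down, withdrawal after a second event and glucose rescue also apply whichever sentence is followed.

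**What to change.** Replace the sentence on cohort totals with: *Counts refer to participants treated at that dose: remove at 2 DLTs when 2-6 have received the dose, 3 when 7-12, 4 when 13-19, and 5 when 20-24; the computed Prob(θ > 0.1) ≥ 0.9 governs.* Label the rows of Table SB1A as number of patients treated at that dose.

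The sponsor should decide explicitly what happens at 1 DLT in 1 participant. The rule as written removes the dose (P = 0.950). Section 6.1.2 has a provision beginning "If a cohort has any DLT, but no dose is dropped", with single DLTs at two doses as its example, but it does not say that a single DLT can never remove a dose. Adding a two-participant minimum would loosen the present rule and should not come in as a side effect of this edit.

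Extending the table to every n from 1 to 24 would help event-driven checks but is optional, since any value can be computed from the stated prior. The cost is one sentence, one row label and one decision, with no extra participants, visits or analyses.
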